--	---

Study schedule overview	
The study schedule consists of the following three phases:
 

1) 14-day outpatient standard therapy phase (Phase 1)

2) 13-week outpatient hybrid closed-loop phase (Phase 2)

o A subset of subjects will participate in 5-days of supervised challenges

o Phase 2 excludes periods due to a study pause

3) 12-month hybrid closed-loop extension phase (Phase 3)

 
Following subject screening, enrollment, and device training, subjects will commence the outpatient standard therapy phase of the study.
 
Current Dexcom G6 CGM users may provide data from a 14-day period within the last 30 days. The CGM data meeting the minimum criteria must be the most recent data from the last 30-days. For non-G6 users, subjects will wear a study CGM, in blinded mode, to record glucose measurements over 14-days while subjects manage their diabetes at home per their usual routine and remaining on their current MDI or pump therapy, and sensor, if applicable, for 14-days.
 
After completion of the standard therapy phase, subjects will be trained on the system and transition to the hybrid closed-loop phase initiating treatment with the Omnipod Horizon™ System. Subjects in each cohort will participate in prescribed challenges during any consecutive 5-day period during Phase 2 of the hybrid closed-loop phase. Subjects who complete Phase 2 can commence their participation in the extension phase (Phase 3).
 
Note: Subjects having completed the prepivotal study may participate in this pivotal study and begin at Visit 5 of Phase 2 (hybrid closed-loop) since Phase 1 (standard therapy) was completed as part of the prepivotal study and is not required to be repeated.

-------------------------	--

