**Table 2: Schedule of Assessments for Phase 1 and Phase 2**

Assessment Schedule	Screening	ST1	ST2	Hybrid Closed-Loop (HCL)											EW a	
	Phase 1 e				Phase 2 c											
Visit Number	1	2	3	4	5 e	6	7	8	9	10	11	12	13	UV b		
Study Day/Visit Window l	-30 to -14d HCL start	-14d to HCL start	-1d to HCL start	1	2 ±1d	3 ±1d	10 ±3d	24 ±3d	38 ±3d	52 ±3d	66 ±3d	80 ±3d	94 ±3d	N/A		
Telephone (T) or Office (O) Visit	O	O	O	O	T/O	T/O f	O									
Laboratory Assessments																
A1c	X													X		
TSH	X															
Creatinine Level	X															
Pregnancy Test	X			X			X		X				X			
Clinical Assessments																
Informed Consent	X				X g											
Medical History (including demographics)	X															
Confirm Eligibility	X				X g											
Concomitant medications	X	X h		X h	X h	X h	X h	X h	X h	X h	X h	X h	X h	X h	X h	
Average total daily insulin (~ 7 days)		X		X												
Average total basal insulin (~ 7 days)		X		X												
Average total bolus insulin (~ 7 days)		X		X												
Pump settings/MDI dosing		X		X												
Height	X													X		
Weight	X													X		
Vital signs	X						X		X					X		
Electrocardiogram d (if applicable)	X															
Adverse events		X	X	X	X h	X h	X h	X h	X h	X h	X h	X h	X h	X h	X h	

Omnipod

Horizon™ Pivotal Study Protocol V5.0

Confidential

Page | 23

Assessment Schedule	Screening	ST1	ST2	Hybrid Closed-Loop (HCL)												EW a
	Phase 1 e				Phase 2 c											
Visit Number	1	2	3	4	5 e	6	7	8	9	10	11	12	13	UV b		
Study Day/Visit Window l	-30 to -14d HCL start	-14d to HCL start	-1d to HCL start	1	2 ±1d	3 ±1d	10 ±3d	24 ±3d	38 ±3d	52 ±3d	66 ±3d	80 ±3d	94 ±3d	N/A		
Telephone (T) or Office (O) Visit	O	O	O	O	T/O	T/O f	O									
Questionnaires																
See Table 4 for specific questionnaires	X	X												X		X
Study Devices																
Training on Glucagon administration and information on treatment of hypo/hyperglycemia		X														
Horizon Data Portal initiation/discontinuation				X										X		X

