### **Pump Naïve Users**

Subjects who are naïve to pump therapy will have the opportunity to participate in a saline trial during the standard therapy phase. A saline trial consists of wearing a cleared Omnipod® DASH System with the Pod filled with saline to simulate pump therapy. This would enable subjects to familiarize themselves with the basic concepts of basal and bolus insulin delivery as well as provide the experience of wearing an on-body device prior to their participation in the hybrid closed-loop phase, if they choose to do so. This is optional and not required. If a pump naïve subject is also a current G6 user that meets the criteria as stated above, the subject will complete the saline trial prior to enrollment in the study.

## 8.1 Visit 2

**Visit 2** represents the commencement of the standard therapy phase. All scheduled assessments will be performed according to Table 2: Schedule of Assessments for Phase 1 and Phase 2. This visit will include:

- Review of concomitant medications
- Average total daily insulin (approximately over the past 7 days)
- Average total daily basal insulin (approximately over the past 7 days)
- Average total daily bolus insulin (approximately over the past 7 days)
- Review of pump settings/MDI dosing
- Assessment of AEs
- Completion of questionnaires (see Table 4: Questionnaires for specific requirements by age group):
  - WHO-5
    - Used to measure current mental well-being
  - EQ-5D
    - Used to measure quality of life
  - T1DDS
    - Used to measure four critical dimensions of distress
  - DTSQs
    - Used to measure satisfaction with diabetes treatment regimens
  - Hypoglycemia Confidence Scale
    - Used to measure hypoglycemia unawareness, hypoglycemia frequency, severity and impact
  - HABS
    - Used to measure critical dimensions of hypoglycemia related concerns and confidence
  - PSQI
    - Used to measure sleep disturbance and usual sleep habits
  - IDSS (T1)
    - Used to measure patient satisfaction with their devices and impact on quality of life
  - SUS
    - Used to measure usability of a system
  - PAID-(Teen, Child)
    - Measures diabetes-related burden
- Training on Glucagon administration and information on treatment of hypo/hyperglycemia

- All subjects are required to have access to glucagon and receive training on how to deliver the medication
- Study device training per manufacturer's instructions (CGM - blinded, BG, and ketone meters)

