- Dispensing of CGM (blinded for non-G6 users), BG, and ketone meter
- QC testing of BG and ketone meter
  - Must pass at least one level of quality control testing prior to dispensing
- CGM sensor placement (Enrollment)
  - Approved anatomical locations for CGM sensor placement will be reinforced as well as the importance of using approved locations

During this visit, subjects will be dispensed the following supplies:

- Dexcom transmitter
- Dexcom receiver
- Dexcom sensors
- Contour® Next One blood glucose meter
- Contour® Next One blood glucose meter test strips
- Contour® Next One blood glucose meter control solution
- Lancets
- Precision Xtra blood ketone meter
- Precision Xtra blood ketone meter test strips
- Precision Xtra blood ketone meter control solution

Subjects will be provided, by the site, information regarding treatment of hypoglycemia and hyperglycemia including sick day management and emergency management of severe hypoglycemia and diabetic ketoacidosis. Subjects will be given contact information for study personnel and product support.

If a subject is on MDI, the investigator will advise the subject on the treatment regimen to reduce insulin depending on the insulin action profile of injected doses prior to the commencement of the hybrid closed-loop phase. MDI subjects will be required to keep a log to record daily doses of insulin during the standard therapy phase.

## 8.2 Visit 3

**Visit 3** will be conducted in person at the clinical study site up to one (1) day prior to the start of the hybrid closed-loop phase. All scheduled assessments will be performed according to Table 2: Schedule of Assessments for Phase 1 and Phase 2. This visit will include:

- Assessment of AEs
- Assessment of whether subjects have met the CGM usage and data criteria

Prior to the commencement of the hybrid closed-loop phase, subjects must meet the following criteria:

- At least 80% CGM use (11.2-days) during any consecutive 14-days in the past 30-days and
- ≥ 2,016 CGM values during the 14-days

If the CGM criteria is not met, the standard therapy phase may be extended up to 30-days, per investigator discretion, or the subject may be withdrawn from the study.

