  - The Pod will be filled with the subject's own U-100 rapid-acting insulin and placed on body. Subjects will also be trained on use of Dexcom G6 CGM, regardless of previous experience, setting up low (recommended to be 70 mg/dL or higher) and high glucose alerts (recommended to be 300 mg/dL or lower) and entering transmitter serial number into the Horizon App.

- Subjects may choose their desired target BG ranging between 110-150 mg/dL in increments of 10mg/dL, although the default and recommended setpoint is 120 mg/dL.
- In addition, Omnipod Horizon™ has a novel bolus calculator feature that incorporates both the CGM value and trend into the suggested bolus amount. In general, if the CGM values are trending up or down, the calculator will add or subtract insulin from the suggested bolus amount to help keep BGs within target range.
- Dispense Omnipod Horizon™ System
- Complaints/device deficiencies for CGM, BG and ketone meter
- Device uploads for CGM, BG and ketone meter
- Data review by clinician
- Removal of the subject's personal insulin pump (if applicable)
  - Investigators may use the Insulet-provided Patient Therapy Order Form (PTOF) as a guide to transition subjects from MDI to pump therapy (Appendix A)

If a subject is a current Dexcom G6 User and Visit 2 and Visit 4 occur on the same day, average total daily insulin and pump settings/MDI dosing only needs to be collected once. Further, if Visit 1 and Visit 4 occur on the same day, only one pregnancy test is required.

At the conclusion of the training and completion of assessments, each subject will initiate their treatment marking their commencement of the hybrid closed-loop phase.

### 9.3 Visit 5

**Visit 5** will be conducted either over the telephone or in person at the clinical study site on Study Day 2 ± 1-day for subjects commencing the hybrid closed-loop phase during Visit 4. For subjects extending their participation from the prepivotal study, the visit may be conducted in person at the clinical study site or over the telephone. This visit will include:

- Informed consent for subjects extending their participation from prepivotal (Informed Consent may occur at any time during the prepivotal study but must occur prior to commencing the pivotal study)
- Establishing eligibility for subjects extending their participation from prepivotal
- Review of concomitant medications
- Assessment of AEs since last visit

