### **12.3.2 Reportable Adverse Events**

Adverse events will be assessed on an ongoing basis throughout the study. Adverse event reporting will begin at the start time of the standard therapy phase (i.e., insertion of the CGM sensor) and continue through the hybrid closed-loop phase 2 and 3 until the subject's participation has ended. All adverse events must be followed until resolution, or until the AE has stabilized, or until the study has been completed.

Pre-existing medical conditions or symptoms observed prior to the start time of the standard therapy phase will not be recorded as an AE and should be collected in the subject's medical history. In the event there is a change (i.e., worsening) in the pre-existing medical condition or symptoms after enrollment meeting the criteria of a reportable adverse event, then an AE must be reported.

For this protocol, a reportable adverse event includes any untoward medical occurrence that meets one of the following criteria:

1. An SAE
2. An ADE unless excluded from reporting in Hypoglycemic Events and Hyperglycemic/Ketotic Events sections below
3. An AE occurring in association with a study procedure
4. An AE not related to a study device issue which leads to temporary or permanent discontinuation of the study device
5. An AE that affects the participant's ability to complete any study procedures
6. An AE for which a visit is made to a hospital emergency department
7. Hypoglycemic Events as defined below
8. Hyperglycemia/Ketotic Events as defined

Skin reactions from sensor or pod placement are only reportable if severe and/or required treatment.

For the purpose of this protocol, mild symptoms of hypoglycemia and hyperglycemia (i.e., clinically non-significant) or blood glucose values out of the normal range (whether or not they resulted in delayed meals or correction boluses) will not be reported as AEs unless determined to meet the reportable criteria in the Hypoglycemic Events and Hyperglycemic/Ketotic Events sections below.

All reportable AEs—whether volunteered by the participant, discovered by study personnel during questioning, or detected through physical examination, laboratory test, or other means—will be reported on an AE eCRF.

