6.2 ANALYSIS OF PERCENTAGE OF TIME IN HYBRID CLOSED-LOOP

The percentage of time in hybrid closed-loop will be calculated as:

$$100 \times \frac{\text{sum of gaps between consecutive CGM readings}}{\text{difference between the earliest and the latest CGM readings}} = \% \text{ time in HCL}$$

A gap is calculated as the difference in time (either minutes or seconds) between two consecutive CGM records as captured by the Horizon™ System. The gaps are then summed to obtain total time in HCL. As records are generally taken in about every 5 minutes, and to ensure that only confirmed HCL records are included, gaps greater than 7 minutes will be excluded from analysis. For the denominator, the chronologically earliest and latest CGM records during HCL as captured by the Horizon™ System will be used.

As opposed to the time in range endpoints, records with no glucose value in the Horizon™ System device output (such as due to an error or device deficiency during which the device does not record glucose readings) will be included in analysis. CGM records reported prior to the start of HCL or after the subject's discontinuation from HCL or during study pause will be excluded from analysis. This endpoint will also be reported separately for the manual and automated modes.

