7.4 CALCULATION OF PERCENTAGE OF TIME IN RANGE

Several effectiveness endpoints involve calculation of percentage of time in a specific glycemic range. These endpoints will be based on the direct output from a device (either a CGM or The Omnipod Horizon™ Automated Glucose Control System). The percentage of time in range (TIR) will be calculated as:

$$100 \times \frac{\text{\# of CGM readings in range}}{\text{\# of evaluable CGM readings}} = \text{TIR\%}$$

The following CGM readings will be excluded from analysis, and therefore, from calculation of TIR endpoints:

- No glucose value is provided in the device output, such as due to an error or device deficiency during which the device does not record glucose readings
- CGM readings reported prior to start of standard therapy phase or after subject's discontinuation from HCL

Statistical Analysis Plan

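### As worded, SAP 7.4 excludes the retrospective 14-day CGM record that the protocol intends as Phase 1 data for exempt Dexcom G6 users

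*SAP*

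**What the plan says.** **Exclusion rule.** SAP 7.4 lists the CGM readings left out of TIR calculations. One bullet covers "CGM readings reported prior to start of standard therapy phase", together with readings after the subject discontinues hybrid closed-loop (HCL). It makes no exception for data recorded before the study, and it sets no minimum number of readings.

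**Start of standard therapy.** SAP 6.4, on insulin requirements, identifies Visit 2 as the start of the standard therapy phase. Protocol 8.1 agrees: Visit 2 "represents the commencement of the standard therapy phase". Protocol 8 has the phase begin once the Visit 2 assessments are complete. Protocol 12.3.2, for adverse-event reporting, ties the "start time of the standard therapy phase (i.e., insertion of the CGM sensor") to an act that Protocol 8.1 lists at Visit 2: "CGM sensor placement (Enrollment").

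**G6 users.** The Protocol Summary states: "Current Dexcom G6 CGM users may provide data from a 14-day period within the last 30 days". Protocol 8 exempts these users from the 14-day study CGM wear if the record shows 80% use and at least 2,016 values, and makes them eligible for Visit 4 at once. Protocol 7.1 describes their standard therapy phase as consisting of Visit 2 alone.

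**Visit timing.** Table 2 lets Visit 2 fall anywhere from minus "14d to HCL start". Footnote k allows Visits 1, 2 and 4 on one day, and Protocol 9.2 plans for it: "If a subject is a current Dexcom G6 User and Visit 2 and Visit 4 occur on the same day", some items are collected only once.

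**Precedence and missing data.** SAP 1 and Protocol 13.11 say the SAP prevails in a discrepancy. SAP 7.5 rules out imputation.

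**The concern.** Each TIR test is a paired comparison of Phase 2 with Phase 1 within subject. A subject without a Phase 1 value contributes nothing to it. SAP 7.4 decides which readings may form that value. For exempt G6 users it cuts at a date that lies after the record the protocol asks them to supply.

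One of the two primary effectiveness endpoints (TIR 70-180 mg/dL) and both secondary endpoints with hypotheses (>180 and <70 mg/dL) rest on this calculation. The subjects concerned are defined by the technology they used at baseline, so a loss would not be a random thinning of the sample. The presentation of TIR by existing G6 use that Protocol 13.5 requires would carry the same gap.

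**Working it through.** **1. The dates, for a G6 user exempt at Visit 2**

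| Item | Where it falls | Source |
|---|---|---|
| Supplied 14-day record | Complete before exemption is granted, so before Visit 2 | Protocol Summary, 5.2, 8 |
| Start of standard therapy | Visit 2 | SAP 6.4; Protocol 8, 8.1 |
| Readings removed | All before that start | SAP 7.4 |
| Start of HCL | Visit 4, same day as Visit 2 or later | Table 2 and footnote k; Protocol 9.2 |

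The whole supplied record lies on the excluded side. No passage moves the start of standard therapy back for these users.

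**2. What survives**

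SAP 6.2 gives the sampling rate: "As records are generally taken in about every 5 minutes".

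- Readings per day: 24 × 60 / 5 = 288.
- Readings in 14 days: 14 × 288 = 4,032.
- 80% use: 0.8 × 14 = 11.2 days, or 0.8 × 4,032 ≈ 3,226 readings.
- The 2,016 minimum: 2,016 / 288 = 7.0 full days.

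Let g be the number of days from Visit 2 to Visit 4. At most 288 × g readings survive. The documents give no gap lengths for exempt users. Table 2 allows g from 0 to 14, so the ceiling runs from 0 to 4,032.

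- g = 0: nothing survives. There is no Phase 1 TIR and, with no imputation, no paired difference. SAP 6.1 and 6.5 carry the same calculation to >180 and <70 mg/dL.
- 0 < g < 7: the surviving readings cannot reach the protocol's own 2,016.
- g < 11.2: they cannot reach 80% use of a 14-day period.

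SAP 7.4 would accept any such fragment, because it sets no minimum.

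**3. Does power suffer?**

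The plan's figure first. SAP 4.1 assumes mean difference 10, SD 15, one-sided alpha 0.0125 and power 90%, and states n = 31. For a paired t-test,

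power = 1 − F(t(0.9875, n−1); n−1, (10/15)√n), with F the noncentral t distribution function.

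This gives 0.894 at n = 30 and 0.905 at n = 31, so 31 is reproduced.

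The share of subjects left without a Phase 1 TIR is not in the documents. Taking it as an assumption, from 200 evaluable subjects:

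| Share lost | n left | Power |
|---|---|---|
| 25% | 150 | >0.999 |
| 50% | 100 | >0.999 |
| 75% | 50 | 0.991 |
| 84.5% | 31 | 0.905 |
| 90% | 20 | 0.706 |

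The break point is (200 − 31) / 200 = 84.5%. The effect falls on who is represented in the TIR analyses, not on overall power.

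**The case against.** The strongest reply is that the supplied 14 days are these users' standard therapy data by design. The protocol offers the record as the alternative to blinded wear, exempts users because they have it, and in 14.2.2 sends standard-therapy CGM data to the comparative analysis. SAP 4.2 defines the change from Phase 1 without naming the Visit 2 date. The 7.4 bullet was probably meant to remove stray readings. On that view there is no discrepancy for the precedence clause to resolve.

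This stands as an account of intent, and an analyst who knew the protocol would probably keep the data. It does not repair the text. The SAP never mentions the retrospective record, its own 6.4 dates the phase from Visit 2, and Protocol 7.1 reduces these users' phase to that visit. A programmer working from the controlling document has no stated basis for keeping the readings. Keeping them would depart from 7.4, and Protocol 13.11 requires deviations from the SAP to be described in the final report.

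A second objection is that fragments are hypothetical, since exempt users may go to Visit 4 immediately. That is fair: nothing shows how often a gap occurs. Protocol 8 also requires the CGM criteria to be met where it discusses which data enter the endpoint analysis, though only for subjects who extend past 14 days. The same-day case needs no assumed gap.

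Third, SAP 4.2 says the primary effectiveness endpoints will not support labeling claims, and SAP 2.5 rests study success on safety rates. This limits the weight of the point but does not make the rule right.

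A reader might also infer that the SAP leaves the start of standard therapy open. It does not: SAP 6.4 settles it, in the direction that creates the conflict.

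**Conclusion.** SAP 7.4 is wrong as written for G6 users exempt at Visit 2. Followed literally, it leaves them with no Phase 1 TIR when Visits 2 and 4 coincide, and otherwise with an interval of no required length in place of the intended 14 days. It should be corrected before analysis.

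The conclusion rests on the start of standard therapy being Visit 2, which both documents state. The reading counts also assume 5-minute sampling with nothing missing, so they are maxima.

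Stronger readings are not supported. A reader might infer that the data will be lost, that the TIR result will be biased in a known direction, or that the trial is underpowered. The documents do not show that the record would be dropped in practice. They give neither the number of exempt users nor how those users differ from the rest. Overall power for TIR 70-180 stays at or above 90% unless more than 84.5% of 200 subjects lose their baseline. A1C does not use CGM data and is unaffected, as are subjects who are not exempt.

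**What to change.** Amend the SAP 7.4 bullet to exclude "CGM readings reported prior to start of standard therapy phase", except the most recent qualifying 14-day record (at least 80% use and at least 2,016 values, within the past 30 days) supplied by exempt Dexcom G6 users, which is their Phase 1 data. Add that only this record is used for their Phase 1 TIR, so that readings between Visits 2 and 4 neither replace it nor are added to it.

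The cost is one clause and one sentence in the SAP, with no new data, visits or change to the tests. The thresholds are already in Protocol 7.1 and 8. This defect calls for no change to the prepivotal, Phase 2 or Phase 3 windows.

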7.5 HANDLING OF MISSING DATA

All practical monitoring and follow-up steps will be taken to ensure complete and accurate data collection. All analyses will be based on available data only; no imputation for missing data is planned.

7.6 EXPLORATORY ANALYSES

The following exploratory analyses will be considered. The analyses may be used for internal research purposes and/or scientific presentations and/or manuscripts and may not all be provided in a regulatory submission:

- Number of hypoglycemic and hyperglycemic events as measured by the system CGM during the hybrid closed-loop phase will be compared to the standard therapy phase
- Glucose metrics from the system CGM during the hybrid closed-loop phase stratified by device mode
- Change from baseline in A1C and BMI at the last follow-up visit, given at least 6 weeks of participation during Phase 2
- Change from baseline in A1C after at least 6 weeks of continuous Phase 2 participation, stratified by baseline A1C (e.g. A1C $\geq 7.5\%$, $\geq 9.0\%$)
- Proportion of subjects with A1C $<7.0\%$ at baseline and after at least 6 weeks of continuous Phase 2 participation; similar analyses using A1C cutoffs of $<7.5\%$, $<8.0\%$ and $<9.0\%$
- Proportion of subjects with change from baseline in A1C after at least 6 weeks of continuous Phase 2 participation of $>0.5\%$ and $>1.0\%$
- Proportion of subjects who either had an improvement from baseline of $>1.0\%$ in A1C or A1C $<7.0\%$ after at least 6 weeks of continuous Phase 2 participation
- Percentage of time the CGM was used during the HCL phase
- Number of meal and correction boluses
- Compare glycemic outcomes (e.g., TIR <70 mg/dL, TIR >180 mg/dL) by bolus frequency per day
- Compare glycemic outcomes (e.g., TIR <70 mg/dL, TIR >180 mg/dL) by use of CGM informed bolus calculator (i.e., days with CGM informed bolus calculator used at least once and days without CGM informed bolus calculator use)
- Post-prandial glucose response including time to peak glucose, peak glucose concentration, peak glucose excursion, to meals with bolus (challenge days 1 and 3) vs no bolus (challenge days 2 and 4)
- Glycemic outcomes and other measures based on evaluable subjects (i.e., those subjects with at least 8 weeks of data during the HCL phase)

Statistical Analysis Plan

The results of exploratory analyses will be presented using summary statistics. Data at Visit 13 will be used for any parameters that are measured at end of Phase 2 (data at Visit 19 will be used for any parameters that are measured at end of Phase 3). Any statistical testing will be performed at a two-sided significance level of 5% with no adjustment for multiple testing. If the observed data are found not to follow a normal distribution, non-parametric methods may be employed (such as Wilcoxon rank sum test as appropriate).

